### 5.1.3 Exploratory Endpoints

- Correlation of biomarker expression levels with antitumor activity and safety.
- Expression levels of biomarkers in blood and tumor samples.
- Correlation of biomarker expression levels with H3B-6527 exposure in plasma.
- H3B-6527 levels in tumor tissue may be assessed.
- H3B-6527 metabolites in plasma and urine.

## 5.2 Study Subjects

### 5.2.1 Definitions of Analysis Sets

**Full Analysis Set (FAS)** will include all subjects who received at least 1 dose of study drug. This will be the primary analysis set for demographic and baseline characteristics. Efficacy analysis will be based on FAS for HCC subjects only.

**Safety Analysis Set** will include all subjects who received at least 1 dose of study drug. This will be the analysis set for all safety evaluations except DLT results.

**DLT Analysis Set** will include all subjects in Dose Escalation phase (Part 1) who are evaluable for a DLT. To be evaluable for a DLT, subjects must have completed safety assessments through predose on C2 Day 1 and must have received at least 17 of 21 (approximately 80%) study days within C1, unless due to a DLT. This will be the analysis set for analyzing DLT results only.

**PK Analysis Set** will include all subjects who have received at least 1 dose of study drug and have at least 1 evaluable plasma concentration.

**Pharmacodynamics Analysis Set** will include all subjects who have received at least 1 dose of study drug and have evaluable pharmacodynamic data.

**PK/Pharmacodynamics Analysis Set** will consist of all subjects in the Safety Analysis Set that also have evaluable plasma PK and pharmacodynamic pretreatment assessment and at least 1 post treatment assessment.

**Response Evaluable Set** will consist of those HCC subjects who have received at least 1 dose of study drug and have measurable disease at baseline and at least 1 post-baseline evaluation.

The number (percentage) of subjects enrolled in the study and included in each analysis set will be summarized.

A listing of subjects included in each analysis set will be provided.

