9 INVESTIGATIONAL PLAN

9.1 Overall Study Design and Plan

This is an open-label, multicenter, Phase 1 study that will be conducted in 2 parts: a Dose Escalation phase (Part 1) and a Dose Expansion phase (Part 2). Approximately 30 to 128 subjects are planned for enrollment. H3B-6527 will be administered by mouth (PO) in 21-day cycles without break to examine both QD and BID dose schedules, with flexibility to also examine additional alternate dosing schedules (eg, daily for 2 consecutive weeks every 3 weeks [dosing on Days 1-14 of a 21-day cycle]).

During both parts of the study, subjects will be administered the study drug with food based on the Healthy Volunteers Food-Effect study (Study H3B 6527-A001-001: A Randomized Phase 1 Food-Effect Study of H3B-6527 in Healthy Subjects). The starting dose of study drug when given with food was agreed upon with the Safety Review Committee (SRC) to meet the criteria that it be no more than one-half of the previously determined safe total daily dose level. Any additional dose escalation will follow the procedures outlined in [Section 9.1.1](#).

The objective of Part 1, the Dose Escalation phase is to determine the MTD and/or RP2D of H3B-6527 in subjects with HCC. The total number of subjects to be enrolled will depend on the observed safety profile, which will determine the number of subjects per dose cohort, as

well as the number of dose escalations required to achieve the MTD and/or RP2D of H3B-6527.

This study makes provision for exploring a BID schedule of H3B-6527; the criteria to evaluate H3B-6527 at the BID dose schedule will be based on an integrated evaluation of safety, tolerability, clinical benefit, PK, and pharmacodynamic data, for all QD dose levels tested. In this case, a new cohort of 3 subjects will be enrolled and treated with a BID dose. The initial total daily dose given BID will be equal to a total daily dose that has been well tolerated as a QD dose (DLT rate <33% in a cohort of 3-6 subjects).

During Part 2, the Dose Expansion phase, a sample size of 40 subjects per dose schedule will be enrolled to examine both QD and/or BID dosing of H3B-6527 based on the recommended dose determined from Part 1, the Dose Escalation Phase. When both dose schedules are accruing subjects, an alternating enrollment schema into QD and BID dose schedule will be followed.

Safety, tumor response, PK, and pharmacodynamic assessments will be performed on every subject; see [Section 9.5](#) for details.

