9.1.1 Study Parts

9.1.1.1 Dose Escalation (Part 1)

The objective of Part 1, the Dose Escalation phase, is to determine the MTD/RP2D of H3B-6527 in subjects with advanced HCC. The selection of the RP2D will be based on an integrated evaluation of safety, tolerability, and clinical benefit, including PK and pharmacodynamic data. The total number of subjects to be enrolled will depend on the observed safety profile, which will determine the number of subjects per dose cohort, as well as the number of dose escalations required to achieve the MTD and/or RP2D of H3B-6527. Assuming 5 dose levels will be studied for the QD dose schedule and 3 dose levels for the BID dose schedule and a maximum of 6 subjects will be enrolled per dose level, approximately 30 to 48 subjects may be accrued during dose escalation. Subjects enrolled into Part 1, Dose Escalation phase, are not required to be FGF19-positive.

The criteria to evaluate at the BID dose schedule will be based on an integrated evaluation of safety, tolerability, clinical benefit, PK, and pharmacodynamic data, for all QD dose levels tested. In this case, a new cohort of 3 subjects will be enrolled and treated with a BID dose. The initial total daily dose given BID will be equal to a total daily dose that has been well tolerated as a QD dose (DLT rate <33% in a cohort of at least 3 subjects). If BID dosing of H3B-6527 is well tolerated in this initial cohort, then dose escalation may continue with BID dosing, following the same dose escalation rules applied to QD dosing. Additional cohorts of subjects may be enrolled to evaluate a less frequent dosing schedule (eg, daily for 2 consecutive weeks every 3 weeks [dosing on Days 1-14 of a 21-day cycle]).

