If PK, pharmacodynamic, or safety data for H3B-6527 suggest that it may be preferable to administer H3B-6527 BID rather than QD, then the dose escalation procedure may be repeated for BID dosing. In this event, a new cohort of 3 subjects will be enrolled and treated with a BID dose; the initial total daily dose given BID will be equal to a total daily dose that has been well tolerated as a QD dose (DLT rate <33% in a cohort of 3-6 subjects). If BID administration of H3B-6527 is well tolerated in this initial cohort, then dose escalation may continue with BID dosing, following the same dose escalation rules applied to QD administration.

Furthermore, additional cohorts of subjects may be enrolled to evaluate a less frequent dosing schedule (eg, daily for 2 consecutive weeks every 3 weeks [dosing on Day -14 of a 21-day cycle]).

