**Table 1 Dose Cohorts in H3B-6527 Dose Escalation Phase**

Dose level	Initial No. of Subjects	H3B-6527 Total Daily Dose
-1	3	150 mg
1 a	3	300 mg
2	3	600 mg
3	3	1000 mg
4	3	1400 mg
5	3	2000 mg

These total daily (dose levels may be evaluated in QD or BID) dose schedules, including intermediate levels, differing MTDs by sub-population (e.g., disease indication or ethnicity), and in expansion of an existing dose level up to 12 evaluable subjects following discussion between the Sponsor and the investigators, if supported by evolving safety, tolerability, PK, and pharmacodynamic data.

a: Planned starting dose level in QD schedule.

Subjects will be assigned to a dose level in the order of study entry. Initially, 3 subjects will be enrolled at the starting dose level. If 2 of the 3 subjects experience a DLT then the dose level -1 (150 mg) will be explored. If 1 of the 3 subjects experiences a DLT then the dose will be expanded to 6 subjects. If  $\geq 2$  of 6 subjects in the starting dose cohort experience a DLT during the first cycle, then the dose level -1 (150 mg) will be explored.

Dose escalation to the next higher dose may proceed if no DLT is observed in C1 among the first 3 subjects accrued to a cohort. If 1 of 3 subjects in the cohort experienced a DLT, up to a total of 6 subjects will be enrolled. If 2 or more of the 3-6 subjects in a cohort experience a

DLT, dose-escalation will cease, and additional subjects will be treated at a lower dose level. Dose escalation will continue until a dose level where 2 or more of 6 subjects experience a DLT.

To be evaluable for a DLT, subjects must have completed safety assessments through predose on C1 Day 1 and must have received at least 17 of 21 (80%) study days within C1, unless due to a DLT. Subjects who discontinue from the study for reasons other than DLT before completing C1 are to be replaced.

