## 5.6 Safety Analyses

All safety analyses will be performed on the Safety Analysis Set and “as treated” basis except the evaluation of DLT and determination of the MTD. The number (percentage) of DLT will be summarized on and the determination of the MTD will be based on DLT Analysis Set in the Dose Escalation part.

Subjects who do not receive study drug for at least 17 of 21 days (80%; not necessarily consecutively) during the first cycle for reasons not considered to be a DLT by both the investigators and the Sponsor will be replaced. The subjects who are replaced will not be considered evaluable for DLT assessments.

Safety data include all AEs, SAEs, clinical laboratory tests, vital signs, ECGs, MUGA/echocardiogram, and ophthalmic examinations.

Safety parameters will be summarized using descriptive statistics (mean, standard deviation, median, Q1, Q3, and range for continuous variables; numbers and percentages for categorical measures).

The effects of H3B-6527 on cardiovascular repolarization will be evaluated via 12-lead continuous cardiac Holter monitoring around first dose administration on C1 Day 1 and Day 8 in the dose escalation part of the study only. Individual ECGs will be extracted from the Holter recordings at specified time points per ECG manual and will be evaluated by a central laboratory. QT intervals will be measured from Lead II and will be corrected for heart rate (QTc) using Fredericia’s (QTcF) correction factors. The primary QTc parameter will be QTcF; secondary parameters (QTc corrected using Bazett’s formula [QTcB], QT, QRS, PR, and heart rate) and wave forms (T waves) will be evaluated.

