## 5.6.2 Adverse Events

The AE verbatim descriptions (investigator terms from the CRF) will be classified into standardized medical terminology using MedDRA. AEs will be coded to the MedDRA (Version 19.0 or higher) lower level term (LLT) closest to the verbatim term. The linked MedDRA preferred term (PT) and primary system organ class (SOC) are also captured in the database.

A treatment-emergent adverse event (TEAE) is defined as an AE that emerges during treatment up to 28 days after last dose, having been absent before treatment or:

- reemerges during treatment, having been present before treatment but stopped before treatment, or
- worsens in severity during treatment relative to before treatment state, when the AE was continuous.

Only TEAEs will be included in summary tables.

The incidence of TEAEs will be reported as the number (percentage) of subjects with TEAEs by SOC and PT. A subject will be counted only once within a SOC and PT, even if the subject experienced more than one TEAE within a specific SOC and PT. The number (percentage) of subjects with TEAEs will also be summarized by highest CTCAE grade.

The number (percentage) of subjects with TEAEs, the number (percentage) of subjects with TEAEs leading to death, the number (percentage) of subjects with SAEs, and the number (percentage) of subjects with TEAEs leading to discontinuation from study drug will be summarized by MedDRA SOC and PT.

Also, the TEAEs will be summarized by relationship to study drug (Yes or No) and by CTCAE grade.

To assess the MTD and DLT, the number (percentage) of subjects with DLT events in each dose level will be summarized.

All AEs will be presented in subject data listings. In addition, listings of DLTs, SAEs, AEs leading to death and AEs leading to discontinuation from study drug will be provided.

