# 6 INTERIM ANALYSES

There will be interim analyses to define the MTDs and/or RP2Ds prior to initiating the Expansion phase of the study. Other interim analyses may be performed to determine if a different dosing schedule (eg, BID) or frequency (eg, 2-weeks on/1-week off) may be preferable. Database locks are not required to perform these analyses. Safety and PK summaries may be provided periodically.

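### The fixed 17-of-21-day rule for DLT evaluability cannot be met on the optional Days 1-14 schedule, and it removes subjects held for 14 days early in Cycle 1 without the reason being reported

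*SAP*

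**What the plan says.** **Evaluability.** SAP 5.2.1 admits a subject to the DLT Analysis Set if safety assessments run to predose on Cycle 2 Day 1 and the subject "must have received at least 17 of 21 (approximately 80%) study days within C1, unless due to a DLT". Protocol 9.1.1.1 says the same. SAP 3.2.2 carries the same day count but a different visit: "must have completed safety assessments through predose on C1 Day 1".

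**Replacement.** Anyone given drug on fewer than 17 of 21 days for a non-DLT reason is replaced: "The subjects who are replaced will not be considered evaluable for DLT assessments" (SAP 5.6; likewise the protocol synopsis, 9.4.4.1, 9.5.5 and 9.7.1.8). Protocol 9.7.1.8 bases the MTD on DLT-evaluable subjects only.

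**Schedules.** Protocol 9.1 plans QD and BID "with flexibility to also examine additional alternate dosing schedules". Protocol 9.4.4.1 adds that "additional cohorts of subjects may be enrolled to evaluate a less frequent dosing schedule", and 9.1.1.1 gives the example "daily for 2 consecutive weeks every 3 weeks [dosing on Days 1-14 of a 21-day cycle". SAP 6 foresees interim analyses on whether a different "frequency (eg, 2-weeks on/1-week off) may be preferable".

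**Hold.** The protocol synopsis and 9.4.8.2 require a 14-day interruption when phosphorus or calcium exceeds a stated limit, with no exception for Cycle 1. Both are measured weekly in that cycle. The synopsis acts on any phosphorus value above the limit; 9.4.8.2 acts on a confirmed value.

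**Display.** SAP 5.6.2 plans that "the number (percentage) of subjects with DLT events in each dose level will be summarized". SAP 5.2.1 plans counts and a listing of membership for each analysis set, and SAP 5 breaks Part 1 outputs down by dose cohort.

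**The concern.** A threshold of 17 dosing days suits a schedule that plans 21. On a schedule that plans 14 it asks for more than the schedule delivers. The only exemption is a shortfall caused by a DLT, so the rule would select subjects on the outcome it is meant to count.

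The hold raises a milder version of the problem on QD and BID. A 14-day interruption takes up two thirds of Cycle 1. A subject held for a possibly drug-related laboratory change, and not judged to have a DLT, is replaced. In a 3+3 design one subject can decide whether the next dose opens, so exclusions of this kind should be visible with their cause.

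The visit named in SAP 3.2.2 matters because, read literally, it asks for no assessment after dosing. It contradicts SAP 5.2.1 on the set used for a primary endpoint.

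**Working it through.** **1. The plan's own figure.** 17/21 = 0.810, and 0.80 × 21 = 16.8, which rounds up to 17. The stated threshold of about 80% reproduces for continuous dosing.

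**2. Days 1-14 schedule.** Maximum dosing days in Cycle 1 = 14, and 14/21 = 0.667. The shortfall is 17 − 14 = 3 days at full compliance. With D subjects having a DLT, however many are treated, the evaluable set is D out of D:

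| DLTs in cohort | Evaluable result | Consequence under 3+3 |
|---|---|---|
| 0 | 0 of 0 | all replaced; cohort never fills |
| 1 | 1 of 1 | the DLT-free subjects are replaced; 1 of 3 or 1 of 6 cannot be reached |
| 2 | 2 of 2 | stop rule met, whatever number was treated |

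Neither 0 of 3 nor 1 of 6, the two results that allow escalation, can be formed.

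**3. A threshold relative to schedule.** 0.80 × 14 = 11.2, which rounds up to 12; 12/14 = 0.857 (11/14 = 0.786 is below 80%). Continuous dosing stays at 17 of 21.

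**4. The 14-day hold under continuous dosing.** Suppose no dose is taken on days k to k+13 and all other doses are taken. Dosing days in Cycle 1 = (k − 1) + max(0, 21 − (k + 13)).

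| Hold starts on day | 1 to 8 | 11 | 12 | 15 | 17 | 18 |
|---|---|---|---|---|---|---|
| Dosing days left | 7 | 10 | 11 | 14 | 16 | 17 |

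Only a start on Day 18 or later keeps the subject at 17. Protocol Table 6 places the post-dose Cycle 1 visits at Day 8 (±3) and Day 15 (±3). A same-day hold therefore leaves 7 to 10 days after the first visit and 11 to 17 after the second.

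**5. Sensitivity to delay between blood draw and hold.** Assumptions, not in the documents: visits spread evenly over the windows, and equal detection at both visits. The share of held subjects falling below 17 days is then 13/14 = 93% with no delay, 12/14 = 86% with 1 day, 11/14 = 79% with 2 and 10/14 = 71% with 3. For Day 15 detections alone it falls from 6/7 = 86% with no delay to 3/7 = 43% with 3 days. The wording conflict on confirmation bears directly on this: a hold from Day 15 leaves 14 days (excluded), whereas a hold delayed to Day 18 leaves 17 (evaluable).

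**6. What one exclusion can do.** Take 1 DLT in 6 evaluable subjects plus one excluded held subject. Stated rule: 1/6 = 16.7%. Counted as a DLT: 2/7 = 28.6%. Counted as DLT-free: 1/7 = 14.3%. Exclusion can therefore raise or lower the apparent rate. At this count it separates one DLT, which allows escalation, from two, which stop it.

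**The case against.** **The cohort is hypothetical.** It is an option that may be used, it lies outside the sample-size assumption of five QD and three BID levels, and Part 2 is planned for QD and BID only. Nothing shows that it was opened. This stands, and it makes the gap latent. It does not remove the gap: the documents name the schedule and give it no evaluability rule of its own. Reading planned rest days as study days does not help, because the replacement sentences count days on which drug was received.

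**The Safety Review Committee is not bound to the count.** It reviews all available safety data and may consider other schedules (protocol 9.1.1.1), and RP2D selection is integrated. This limits the consequence, but the MTD is still defined on evaluable subjects.

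**An intermittent cohort would always stop.** A reader might infer that the stop rule is met there at any dose. That needs two DLTs; without them the cohort simply does not fill.

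**The exclusions are hidden.** A reader might infer this too, but it is wrong as a general statement. Safety Analysis Set count minus DLT Analysis Set count gives the number removed per dose cohort, and membership is listed. SAP 5.6.1 also counts treatment delays due to adverse events. What no planned output states is the reason for exclusion, which would have to be pieced together from the dosing, adverse event and laboratory listings.

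**Held subjects often become DLTs anyway.** Partly true. Table 2 makes many Grade 3 or higher nonhematologic events DLTs, and its Grade 2 clause covers related events that force a dose reduction or fewer than 17 days. But that clause is discretionary, and isolated symptom-free Grade 3 laboratory elevations lasting 7 days or less are exempt. No passage links the hold to Table 2.

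**Conclusion.** The main point holds by day counting alone: 14 is less than 17, so a DLT-free subject on Days 1-14 can never be evaluable, and 3+3 cannot be run in such a cohort as written. It is conditional on that cohort being opened. QD and BID are not affected by it.

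The visit named in SAP 3.2.2 is a plain contradiction with SAP 5.2.1 and protocol 9.1.1.1.

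The secondary point holds in a limited form. A hold starting before Day 18 of Cycle 1 takes a subject without a declared DLT out of the MTD denominator, and the reason is not reported. It would be tempting to say that most held subjects are lost, or that the MTD is biased. The first depends on a delay from draw to hold that the documents do not fix. The second is not shown: they give no hold rate, and the direction could go either way.

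**What to change.** 1. In the evaluability and replacement sentences (SAP 3.2.2, 5.2.1 and 5.6; protocol synopsis, 9.1.1.1, 9.4.4.1, 9.5.5 and 9.7.1.8), state the threshold as at least 80% of the Cycle 1 dosing days planned for the assigned schedule: 17 of 21 for continuous QD and BID, as now, and 12 of 14 for Days 1-14. Keep the exception for shortfalls due to a DLT.
2. The Grade 2 clause in protocol Table 2, the synopsis table and SAP Table 2 carries its own fixed 17 days. On Days 1-14 every subject falls short of that by design, so the sponsor must reconcile it with the new threshold.
3. In SAP 3.2.2, replace Cycle 1 Day 1 with Cycle 2 Day 1.
4. Add to the DLT table, per dose level, the number of subjects excluded because Cycle 1 doses were withheld for a drug-related event. Keep the stated rule as primary. A DLT rate with these subjects counted each way is optional.
5. The sponsor must reconcile the two versions of the phosphorus trigger (synopsis and 9.4.8.2), and the hold with Table 2 and the replacement rule. No clinical rule is proposed here.

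Cost: a few sentences in each document and one table line. Rounding up puts 12 of 14 at 86%, slightly above 80%. The present day count does not say whether a BID day with one missed dose counts as a dosing day; this change leaves that as it is.

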The RP2D may not exceed the MTD and will be agreed upon by the SRC, based on an integrated evaluation of safety, tolerability, clinical benefit, PK, and pharmacodynamic data, for all dose levels tested. Clinically significant toxicities (eg, chronic Grade 2 toxicities) or AEs that meet the definition of dose limiting but occurring after C1 (dose-modifying events,

DME) may be considered when determining the RP2D. Once the MTD/RP2D is reached, at least 6 HCC subjects must be enrolled at the RP2D (regardless of the total number of subjects enrolled at that dose level) to proceed with dose expansion.

To be evaluable for a DLT, subjects must have completed safety assessments through predose on C2 Day 1 and must have received at least 17 of 21 (approximately 80%) study days within C1, unless due to a DLT. Subjects who discontinue from the study for reasons other than DLT before completing C1 are to be replaced. Subjects who experience toxicities meeting DLT criteria during C1 will be discontinued from treatment. In rare cases, an exemption to study discontinuation for a DLT in 1st cycle may be considered after discussion between the treating physician, Sponsor and study medical monitor. Subjects who experience toxicities meeting DLT criteria may, at the discretion of the investigator and after discussion with the Sponsor, be allowed to continue study drug at a reduced dose if this is judged to be in the best clinical interest of the subject. The Sponsor will communicate information about DLTs or safety concerns rapidly to all sites as per the separate Dose Escalation Plan, which also details the format and timelines of the Dose Escalation review meetings, and the communication of dose level decisions to all sites.

9.1.1.1.1 **DEFINITION OF DOSE-LIMITING TOXICITIES OR DOSE-MODIFYING EVENTS**

DLTs are defined as any of the toxicities listed in Table 2 occurring during C1 Phase 1 only and judged by the investigator as related to study drug (ie, assessed as unrelated to disease, intercurrent illness, or concomitant medications). Any event that occurs in C2 or beyond (including any cycle in Phase 2) will be considered a DME.

Table 2 Definition of Dose-Limiting Toxicity (Cycle 1 Phase 1 Only) or Dose-Modifying Event (Cycle 2 or Beyond and Any Cycle in Phase 2)

TOXICITY	CRITERIA

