Management of hyperphosphatemia or hypercalcemia: Phosphorus and calcium will be measured at screening, before the first dose, every week with safety labs during C1, and on Day 1 and Day 8 for C2 and beyond. Please note that a treatment cycle is 21 days. Subjects with elevated levels of phosphorus or calcium at screening, as defined as being over the ULN on local lab ranges, may not participate in this study and should be referred for management of such. If successfully controlled, subjects may be rescreened. During study participation, any confirmed levels of phosphorus above 7 mg/dL, or calcium equal to or above Grade 2 hypercalcemia as per CTCAE, Version 4.03, will result in the dose of H3B-6527 being held for 14 days. The hyperphosphatemia and / or hypercalcemia should be managed by local practice, with medication, diet change and potential referral as necessary. After 14 days of holding the drug, if the phosphorus level has returned to 5.5 mg/dL or lower, and the calcium is less than or equal to a Grade 1 elevation, the subject may begin taking H3B-6527 again at one dose level lower than their original dose and should continue other measures initiated during the drug holiday, such as phosphorus lowering agents, while on study. If a subject should experience hyperphosphatemia above 7 mg/dL or hypercalcemia equal to or above Grade 2 again on study, then study therapy will be discontinued.

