9.7.1.8 Safety Analyses

Evaluation of safety will be performed on the Safety Analysis Set except for the determination of the MTD during the dose escalation. The determination of the MTD will be based on all DLT-evaluable subjects enrolled in the Dose Escalation part.

Subjects who do not receive study drug for at least 17 of 21 days (approximately 80%; not necessarily consecutively) during the first cycle for reasons not considered to be a DLT by both the investigators and the Sponsor will be replaced. The subjects who are replaced will not be considered evaluable for DLT assessments.

Safety data to be evaluated include AEs, clinical laboratory results, vital signs, ECGs, and the results of ophthalmic examinations.

Safety parameters will be summarized using descriptive statistics (mean, standard deviation, median, Q1, Q3, and range for continuous variables; numbers and percentages for categorical measures).

The effects of H3B-6527 on cardiovascular repolarization will be evaluated via 12-lead continuous Holter/ECG monitoring on C1 Day 1 and on Day 8 in the Dose Escalation phase

of the study only. Individual ECGs will be extracted from the Holter recordings at specified time points per ECG manual and will be evaluated by a central laboratory. QT intervals will be measured from Lead II and will be corrected for QTcF correction factors. The primary QTc parameter will be QTcF; secondary parameters (QTcB, QT, QRS, QTcB, PR, and heart rate) and waveforms (T waves) will be evaluated.

9.7.1.8.1 **EXTENT OF EXPOSURE**

Descriptive statistics for subjects treated, including the duration of treatment, the number of cycles received, and the number of subjects requiring dose changes, will be presented. A by-subject listing of the date of study drug administration and the dose administered will be presented.

9.7.1.8.2 **ADVERSE EVENTS**

The AE verbatim descriptions (investigator terms from the CRF) will be classified into standardized medical terminology using the Medical Dictionary for Regulatory Activities (MedDRA). AEs will be coded to the MedDRA (Version 18.0 or higher) lower level term closest to the verbatim term. The linked MedDRA PT and primary system organ class (SOC) are also captured in the database.

A treatment-emergent adverse event (TEAE) is defined as an AE that emerges during treatment, having been absent at pretreatment (Baseline) or

- Reemerges during treatment, having been present at pretreatment (Baseline) but stopped before treatment, or

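### DLT evaluability depends on why Cycle 1 days were missed, so a DLT in a subject already short of 17 days for another reason is left out of the MTD count

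*SAP*

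**What the plan says.** The DLT Analysis Set in SAP 5.2.1 requires safety assessments through predose on Cycle 2 Day 1, and that subjects "must have received at least 17 of 21 (approximately 80%) study days within C1, unless due to a DLT". Protocol 9.1.1.1 carries the same condition and adds: "Subjects who discontinue from the study for reasons other than DLT before completing C1 are to be replaced".

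SAP 5.6 restates it as a replacement rule. Subjects short of 17 of 21 days "during the first cycle for reasons not considered to be a DLT by both the investigators and the Sponsor will be replaced", and then: "The subjects who are replaced will not be considered evaluable for DLT assessments". Protocol 9.4.4.1, 9.5.5 and 9.7.1.8 say the same.

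The primary endpoint is counted on that set. SAP 5.6 says that "the determination of the MTD will be based on DLT Analysis Set in the Dose Escalation part"; protocol 9.7.1.8 says: "The determination of the MTD will be based on all DLT-evaluable subjects enrolled in the Dose Escalation part".

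Three other texts bear on the point:
- The escalation steps and Table 3 in protocol 9.4.4.1 count DLTs among the subjects of a cohort and do not limit the count to evaluable subjects.
- Table 2 in both documents lets a drug-related Grade 2 nonhematologic toxicity that leads to fewer than 17 dosing days be deemed dose-limiting, if investigators and Sponsor agree.
- Protocol 9.1.1.1 and 9.4.2 normally end treatment after a Cycle 1 DLT.

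No section says that a subject with a Cycle 1 DLT is evaluable whatever the number of days dosed.

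**The concern.** An exposure minimum exists so that a subject who took too little drug is not counted as having tolerated the dose. It has no purpose for a subject who has already had a DLT, and the exception suggests that the authors meant such subjects to count. As worded, though, the exception asks whether the DLT caused the missed days. If the days were missed for something else and a DLT then follows, the rule removes an observed, drug-related Cycle 1 toxicity from the primary endpoint.

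A single event decides each step of a 3+3 design: none in 3 escalates, 1 in 3 expands the cohort, and 2 or more stops escalation. One omitted DLT can therefore matter.

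**Working it through.** **1. The threshold.** 17/21 = 80.95%, which agrees with the stated approximate 80%. Up to 21 − 17 = 4 days may be missed. With 5 missed, 16/21 = 76.2% and the subject is short.

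**2. Three records read against the rule.**
- *A.* Dosed Days 1 to 7, then held from Day 8 for confirmed phosphorus above 7 mg/dL. Protocol 9.4.8.2 says such a level "will result in the dose of H3B-6527 being held for 14 days", so 21 − 14 = 7 dosing days are possible. Day 15 laboratory tests show drug-related ALT of 6 × ULN from a normal baseline, which meets the hepatic row of Table 2. Days 8 to 14 were already missed, so at most 14 of 21 days could have been dosed in any case. The shortfall was fixed before the DLT and cannot be due to it. Unless the hold is itself adjudicated as a DLT, the subject is replaced and not counted.
- *B.* Stops drug on Day 12 for early progression (at most 12 days dosed) and has drug-related Grade 4 thrombocytopenia on Day 16. Adverse events are collected to 30 days after the last dose (protocol 9.5.1.4.1), so the event is recorded and falls in Cycle 1. The 17-day rule excludes the subject.
- *C.* A DLT on Day 10 stops dosing. The shortfall is due to the DLT, and the subject counts.

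**3. Effect on one cohort**, if the replacement has no DLT and the evaluable count is followed.
- Three subjects, one DLT omitted: 0/3 after replacement (escalate). Counted: 1/3 (expand), or 1/4 = 25.0% if the replacement is already enrolled.
- Six subjects, a second DLT omitted: 1/6 = 16.7% after replacement (MTD criterion met). Counted: 2/6 = 33.3%, or 2/7 = 28.6% with the replacement. Either way there are 2 DLTs, which stops escalation.

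**4. Sensitivity if only DLT subjects are dropped.** Let p be the true DLT rate and f the share of DLT subjects dropped. The documents give no value for f. Evaluable rate p′ = p(1 − f)/(1 − pf). Probability of clearing a level = q³ + 3p′q²·q³, with q = 1 − p′. For p = 0.33 and f = 10%: p′ = 0.297/0.967 = 0.307, and the probability is 48.0%.

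| True rate | f = 0 | f = 10% | f = 20% |
|---|---|---|---|
| 30% | 49.4% | 53.9% | 58.8% |
| 33% | 43.4% | 48.0% | 53.0% |
| 40% | 30.9% | 35.1% | 40.1% |

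This table assumes that no subject without a DLT is dropped.

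**5. Sensitivity if shortfall is independent of DLT.** Let s be the share of all subjects falling short for a non-DLT reason. The current rule drops both kinds of subject: p(1 − s)/[p(1 − s) + (1 − p)(1 − s)] = p. The expected rate is unchanged.

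**6. The corrected rule under the same independence.** Every DLT counts and short-exposed subjects without a DLT are replaced: p/[p + (1 − p)(1 − s)]. For p = 0.30:
- s = 10%: 0.30/0.93 = 32.3%, and the escalation probability falls from 49.4% to 44.9%.
- s = 20%: 0.30/0.86 = 34.9%, and it falls to 39.9%.

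**The case against.** The strongest reply is that the gap rarely opens and that other safeguards stand behind it.

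- *The usual case works.* A Cycle 1 DLT normally ends treatment, so later missed days are due to it. This stands. The gap needs at least 5 days missed for another reason and a separate DLT in the same subject.
- *Table 2 may rescue record A.* Focal mineralization with associated hyperphosphatemia is a foreseen drug effect (protocol 7.1.1.3) and the calcium hold starts at Grade 2, so a mineral hold could be adjudicated as dose-limiting. Replacement also needs a judgement that the reason is not a DLT. This stands in part: the clause is discretionary and does nothing for record B. A reader might infer that every subject on a mineral hold is automatically replaced; the documents do not say so.
- *Record B has not left the study.* Protocol 9.5.5 separates stopping drug from stopping participation, so the clause on leaving the study need not apply. This stands, but the 17-day rule reaches record B by itself.
- *The decision makers see the event.* The Safety Review Committee reviews all available safety data, the RP2D rests on an integrated evaluation, DLTs are listed, and treatment-emergent events are tabulated on the Safety Analysis Set. Protocol 9.1.1.1 also refers to a separate Dose Escalation Plan that is not among these documents. A reader might infer that the event vanishes or that the decision must change. Neither follows. The formal DLT table and MTD count would still omit it, while the cohort wording in protocol 9.4.4.1 would appear to include it.

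**Conclusion.** Wrong as written, moderate severity. The literal rule can drop an observed, drug-related Cycle 1 DLT from the primary endpoint, and it conflicts with the cohort count in the escalation steps.

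Its size is at most one decision in an affected cohort: 0/3 in place of 1/3, or 1/6 in place of 2/6. That depends on the replacement subject having no DLT and on the committee following the evaluable count. How often the overlap occurs cannot be derived from the documents.

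A reader might also infer that the error always runs towards a higher dose. Each omitted DLT does lower that cohort's count. But holds and early progression also remove subjects without a DLT, and under independence the expected evaluable rate does not move. The rises in step 4 are what-if figures for the case where only DLT subjects are lost. No sample size figure depends on this point.

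**What to change.** In SAP 5.2.1 and 5.6 and protocol 9.1.1.1, 9.4.4.1, 9.5.5 and 9.7.1.8, state:

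> Any Part 1 subject who experiences a DLT in Cycle 1 is included in the DLT Analysis Set regardless of days dosed, reason for missed doses, or completion of the Cycle 2 Day 1 assessments. The 17-of-21-day and Cycle 2 Day 1 conditions, and replacement, apply only to subjects without a DLT.

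Reconcile the escalation steps and Table 3 in protocol 9.4.4.1 with this, so that the escalation count and the DLT table use the same subjects. SAP 3.2.2 and the protocol synopsis repeat the rule and should follow. The change concerns counting only and alters no dose, hold or stopping rule.

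It needs a sentence in each place and no new data. The statistical cost is an upward push on the observed DLT rate, because short-exposed subjects without a DLT are still replaced. Under independence, a true 30% with 10 to 20% shortfall appears as about 32 to 35%, and the chance of escalating falls from 49.4% to about 45 to 40%. That is a conservative error, and the SAP should acknowledge it.
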